- Length of hospital stay defined in days from POD 1 to until hospital discharge excluding death

Safety Measures

The following description were based on the original protocol.

Adverse Events (AE)

An AE is any untoward medical occurrence in a subject to whom an intervention has been administered, including occurrences which are not necessarily caused by or related to that intervention. An AE can therefore be any unfavorable and unintended sign, symptom or disease temporarily associated with study activities. However, this study does not involve an investigational medical device, and all trial interventions are already in routine clinical use for patients undergoing a surgical procedure. The safety of the intervention will be monitored by recording acute adverse events at 24 hours and 30 days after randomization as a trial outcome. These events will be monitored at intervals by the DMEC and will be recorded separately as an AE on the CRF.

Serious Adverse Event (SAE)

A serious adverse event (SAE) is defined as an untoward occurrence that:

- results in death
- is life-threatening
- requires hospitalization or prolongation of existing hospitalization significantly beyond normal inpatient stay for the surgery concerned
- results in persistent or significant disability or incapacity

An SAE occurring to a research participant should be reported to the sponsor where in the opinion of the Chief Investigator the event was:

- Related – that is, it resulted from administration of any of the research procedures, and
- Unexpected – that is, the type of event is not listed in the protocol as an expected occurrence.

This study is an investigation of a perioperative intervention. It is expected that patients undergoing major surgery will suffer complications, with consequences up to and including death. Only complications considered by the Chief Investigator to be *related to the use of study procedures* and not a typical surgical complication should be reported as SAEs.

Study Design

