Stage	Target Information (%)	N1	N2	Efficacy Boundary (Critical Z-value scale)	Alpha Spent	Futility Boundary	Beta Spent	Power
1	33%	309	309	±3.710	0.0002		0	-

[figure not shown]
2	67%	618	618	± 2.511	0.0119	± 1.157	0.0828	-
3 (final)	100%	927	927	± 1.932	0.0379	± 1.932	0.1172	0.803

Note: O'Brien-Fleming Analog alpha and beta spending function is adopted

The trial could be stopped for efficacy if the efficacy boundary is crossed at first ($Z < -3.71$, $\alpha < 0.0002$) or second ($Z < -2.51$, $\alpha < 0.0119$) interim analysis, respectively (Figure 1). We will evaluate the combined outcome incidence at the first intermediate analysis and increase sample size at that point if it proves to be lower than anticipated.

If the futility boundary is not crossed ($-1.16 < Z < 1.16$) at second interim analysis, and the study will continue if there is no safety concern. If needed, the sample size of the study might be re-estimated by the DSMB statistician using the observed aggregated data (not the treatment effect) using the conditional power analysis at the interim analysis stage. Since the futility boundary is assumed non-binding, even it is crossed, the DSMB will make recommendation on whether or to stop the trial taking in consideration the totality of accumulated evidence, including the patient accrual rate, observed treatment effect, etc. The whole evaluation will be conducted in a blinded manner.

Figure 1. Group sequential plot

Two interim analyses were performed as per the protocol. No stopping rules were triggered and the DSMB recommended continuing at each analysis. Therefore, the trial proceeded and

finished.

Analysis Populations

Intention-to-Treat (ITT) population: All randomized patients having at least some outcome data will be included in the analysis in the groups to which they were randomized, regardless of the care they received.

Per-Protocol (PP) population: This analysis includes patients, as long as they have outcome data, who completed the study in accordance with the protocol. The patient in the intervention group is determined to have received the intended intervention if their NIRS measurements during the intervention time window are within 90-110% of the baseline value for 80% of the time. The purpose is to assess the effect of the intervention under optimal conditions.

[figure not shown]
Documentation of Deviations:

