- All protocol deviations will be documented in a protocol deviation log, which will be reviewed regularly by the trial steering committee to ensure consistency in applying the exclusion criteria.
- The rationale for excluding each participant will be documented in detail.

The primary analyses of the primary and secondary outcomes will be based on the ITT population. The per-protocol population will be used in the safety and sensitivity analysis.

Note: Patients who were randomized and treated, but lost to follow up, will be included to the time of dropout. Patients who withdrew their consent to participate the study will not be included in analysis.

The CONSORT diagram as of January 26, 2024 is presented as follows. The last patient was recruited on December 27, 2023. At the time of formulating this statistical analysis plan, the follow-up per research protocol is ongoing. We anticipated to finish patient follow-up in early February 2024.

We will evaluate the baseline homogeneity using absolute standardized differences. For both primary and secondary analyses, we will correct for baseline factors with ASDs above the threshold determined by the following equation: $1.96 \times \sqrt{(\text{nt} + \text{nc})/(\text{nt} * \text{nc})}$.1 where t is treatment and c is control.

Analysis of the primary outcome

The primary outcome will be evaluated using logistic regression to estimate the odds of postoperative composite complications. A one-sided Z-value < -1.932 will be considered statistically significant.

A sensitivity analysis evaluating an average relative effects model. (Edward J Mascha, Daniel I Sessler. Statistical grand rounds: design and analysis of studies with binary- event composite endpoints: guidelines for anesthesia research. *Anesth Analg*. 2011 Jun;112(6):1461-71. doi: 10.1213/ANE.0b013e31821796d3.)

Analysis of the secondary outcomes

For the secondary analysis of continuous and categorical outcomes in the BOTTOMLINE-CS trial, the following details will outline the statistical methods that will be used. All analyses will be adjusted for unbalanced baseline characteristics and reported with 95% confidence intervals.

- Continuous outcomes will be analyzed using linear regression or generalized linear models as appropriate, depending on the distribution of the data and the study design.
- Composite secondary outcomes will be analyzed using the same approach as the primary outcome.

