- Categorical outcomes will be analyzed using logistic regression for binary outcomes or chi-squared tests for categorical variables with more than two categories.
- Bonferroni-Holm's method will be used for multiplicity adjustment for the p values of those secondary outcomes.

Safety analysis

- This analysis will list all adverse events and serious adverse events that were related to the research procedures.
- The analysis will include rows for each type of adverse event and columns for the intervention group, control group, number of events, percentages, and a comparison column if appropriate.

Sensitivity Analysis

Patients who withdrew from the trial voluntarily will not be included in analysis.

In the sensitivity analyses, we will assess the robustness of the trial findings. These analyses deal with the patients who did not have outcome data and the per-protocol population instead of ITT population. The plan for conducting sensitivity analyses in the BOTTOMLINE-CS trial are outlined as follows:

Missing Data:

- In the analyses of the primary and secondary outcomes as detailed above, we will exclude patients without outcome data. This approach corresponds to missing completely at random (MCAR).
- Under the missing at random (MAR) assumption, we will use Markov Chain Monte Carlo (MCMC) for multiple imputation approach with 20 imputed copies. Standard multiple imputation methods will be adopted.
- Under the missing not at random (MNAR) assumption, we will use the following methods.
 - Best-case and worst-case scenario analysis: For binary outcomes, we will impute all missing outcomes as successes in the intervention group and failures in the control group for the best-case scenario and the opposite for the worst-case scenario.
 - Pattern-mixture models: These models will be used to explore the impact of different missing data patterns on the results.
 - Selection models: We will fit models that make specific assumptions about the mechanism of missingness, such as logistic regression models that include a term for whether data are missing or observed.

Analysis based on the per-protocol population

The above specified analyses for the primary and secondary outcomes will be repeated using the per-protocol population.

Reporting of Sensitivity Analyses:

- Results will be reported focusing any changes in significance or the magnitude of the treatment effect compared to the results of the primary analyses specified above.

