- Each secondary outcome will be listed with its respective statistical analysis results.
- We plan to move this table to supplementary material as we plan to present the results using a forest plot. The final decision will depend on the journal style.

Table 4: Safety Outcomes

- This table will list all adverse events and serious adverse events reported during the trial. If there are too many AEs to include in the main text, this table will be moved to the supplementary material.
- The table will include rows for each type of adverse event and columns for the intervention group, control group, number of events, percentages, and a comparison column if appropriate.

Figure 1: CONSORT Flow Diagram

- The flow diagram will provide a visual representation of participant flow through the trial, including enrollment, allocation, follow-up, and analysis.
- It will have boxes for each phase and arrows indicating the movement of participants, with numbers for each group at each stage.

Figure 2: Forest plot of the primary and secondary outcomes.

- This figure will present the results of primary and secondary analyses.
- The forest plot will include lines for each subgroup with squares representing the effect estimate (e.g., odds ratio) and horizontal lines representing the 95% confidence intervals.
- A vertical line will represent no effect, and a diamond at the bottom will represent the overall effect size.
- The style of presentation will be similar to the following figure.

[figure not shown]

Figure 3: Forest Plot for Subgroup Analysis

- This figure will present the results of pre-specified subgroup analyses.
- The forest plot will include lines for each subgroup with squares representing the effect estimate (e.g., odds ratio) and horizontal lines representing the 95% confidence intervals.
- A vertical line will represent no effect, and a diamond at the bottom will represent the overall effect size.

Appendices

Inclusion of the SAP approval form, mock tables and figures, and any relevant statistical code.

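### The safety analysis is assigned to the per-protocol population, which leaves out exposed intervention patients who missed the saturation target

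*SAP*

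**What the plan says.** The last part of Analysis Populations gives the intention-to-treat (ITT) set to the primary analyses of the primary and secondary outcomes. It then adds: "The per-protocol population will be used in the safety and sensitivity analysis".

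The two sets are defined a little earlier in the same section:

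- **ITT:** "All randomized patients having at least some outcome data will be included in the analysis in the groups to which they were randomized", whatever care they received.
- **Per-protocol:** patients with outcome data who completed the study according to protocol. An intervention patient is counted as properly treated only "if their NIRS measurements during the intervention time window are within 90-110% of the baseline value for 80% of the time". The aim is given as: "The purpose is to assess the effect of the intervention under optimal conditions".

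Three later places bear on the point:

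- The Safety analysis section names no population. It says: "This analysis will list all adverse events and serious adverse events that were related to the research procedures".
- Table 4: Safety Outcomes says: "This table will list all adverse events and serious adverse events reported during the trial".
- The section on the per-protocol analysis does not mention safety. It says: "The above specified analyses for the primary and secondary outcomes will be repeated using the per-protocol population".

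**The concern.** A safety comparison should count everyone exposed, under the same rule in both arms. The per-protocol set does neither. A patient managed under the saturation-guided protocol whose readings strayed from the target was still exposed to whatever was done to correct them. Removing that patient conditions the safety result on how the patient responded, and the saturation rule is stated for one arm only.

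The set also has an efficacy purpose, namely the effect under ideal conditions. That fits poorly with safety reporting in a trial the SAP describes as pragmatic.

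At stake are the adverse event (AE) and serious adverse event (SAE) tables. These are where harms outside the primary composite and the secondary outcomes would appear.

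**Working it through.** **1. The text.** The SAP states no size for the safety set and no attainment rate, so there is no figure of its own to reproduce. The finding rests on setting the sections side by side.

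| SAP section | Population for safety | Events covered |
|---|---|---|
| Analysis Populations | Per-protocol | not stated |
| Safety analysis | none named | AEs and SAEs related to the research procedures |
| Table 4: Safety Outcomes | none named | all AEs and SAEs reported |
| Analysis based on the per-protocol population | safety not mentioned | primary and secondary outcomes only |

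Only the first row names a population. Table 4 cannot hold every reported event if it is restricted to that population. The note that follows in Analysis Populations keeps treated patients who are lost to follow-up until they drop out. That also sits badly with a set that requires study completion.

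**2. Inputs for the illustration.**
- Planned intervention patients: 980 (Sample Size Determination).
- Evaluable intervention patients: 927 (final-stage N per arm in Table 1 of Interim Analysis).
- Share missing the saturation target, m: not in the SAP; assumed 10% to 40%.
- True rate of a rare event: assumed 0.1%.

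**3. Patients lost and precision.** Dropped = n × m. For an event type with no cases among n patients, the one-sided 95% upper bound on its rate is 1 − 0.05^(1/n).

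| m | Dropped / kept of 980 | Bound | Dropped / kept of 927 | Bound |
|---|---|---|---|---|
| 0% | 0 / 980 | 0.305% | 0 / 927 | 0.323% |
| 10% | 98 / 882 | 0.339% | 93 / 834 | 0.359% |
| 20% | 196 / 784 | 0.381% | 185 / 742 | 0.403% |
| 30% | 294 / 686 | 0.436% | 278 / 649 | 0.461% |
| 40% | 392 / 588 | 0.508% | 371 / 556 | 0.537% |

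The chance of seeing at least one case at a true rate of 0.1% is 1 − 0.999^n. With 980 patients it is 62%. With 882 it is 59%, and with 588 it is 44% (1 − 0.999^588 = 0.4447).

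**4. Direction of bias.** Let k be the event risk in patients who missed the target divided by the risk in those who met it. The per-protocol rate in the intervention arm, relative to the rate in all its patients, is 1 / ((1 − m) + m·k).

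| m | k = 0.5 | k = 1 | k = 2 |
|---|---|---|---|
| 20% | 1.11 | 1.00 | 0.83 |
| 40% | 1.25 | 1.00 | 0.71 |

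The intervention could look safer or less safe than it is, depending on k, which the SAP does not give.

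**5. Scope of events.** The Safety analysis section can be read as covering only procedure-related events, whereas Table 4 covers all reported events. For SAEs the two nearly coincide, because the SAE section says that only complications judged related to study procedures "and not a typical surgical complication should be reported as SAEs". The ambiguity is therefore about the other AEs.

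**The case against.** The best defence is that the sentence does not say the per-protocol set is the only one used for safety. For sensitivity it plainly is not the only one, since the missing-data analyses concern patients whom the per-protocol definition excludes. On that reading, per-protocol safety is an extra analysis and Table 4 stands. This does not rescue the text. The preceding sentence limits ITT to the primary and secondary outcomes, so an extra per-protocol analysis would leave safety with no main population at all.

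It can also be said that the ITT set requires some outcome data, so a treated patient with an AE and nothing else might still be missed. The Adverse Events section answers this: acute adverse events are recorded as a trial outcome, so a patient with a recorded event has outcome data.

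Two qualifications are fair. Controls are not without any criterion, because the general requirement of completing the study according to protocol applies to both arms; what is one-sided is the saturation rule. And the practical reach is limited: death and the major cerebral, cardiac, respiratory, renal and infectious complications belong to the primary composite and are analysed by ITT.

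**Conclusion.** The point holds and should be corrected. As written, the SAP bases safety on a set selected by a post-randomisation response in one arm, and this conflicts with its own Table 4. That the set drops patients who missed the target is an inference, but a direct one: the saturation criterion is the only operational rule given for the intervention arm.

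The sizes are illustrative and depend on the assumed 10% to 40% missing the target and on the assumed event rate. The contradiction in the text depends on neither. No direction of bias is claimed. The effect is confined to the AE and SAE tables, and the ITT analyses of the primary and secondary outcomes are not touched.

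**What to change.** - In Analysis Populations, delete the reference to safety from the sentence on the per-protocol set, so that this set serves sensitivity analyses only.
- In the Safety analysis section and in Table 4, name the ITT set already defined: patients as randomised, with the same rule in both arms. State there that a recorded AE counts as outcome data.
- Make the two descriptions of the listing agree: tabulate all recorded AEs and the reported SAEs by arm, and show relatedness where it was recorded.

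The cost is a few lines of SAP text and a slightly larger safety table. AEs are already recorded on the case report form, so no new data are needed. The SAP's separate exclusion of patients who withdrew consent is not altered by this change.

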Off-pump CABG is performed to improve cardiac blood flow without the use of a cardiopulmonary bypass machine which may provoke complications including stroke, renal failure, and blood loss. Despite potential benefits, off-pump surgery can cause complications including graft occlusion, myocardial infarction, and neurocognitive deficits. The prevalence of such complications varies widely in the literature, with some studies suggesting it ranges from 5% to 30%, influenced by patient comorbidities and surgical technique. Continuous monitoring of tissue oxygenation may reduce the incidence of such complications by enabling the early detection and correction of tissue hypoperfusion. This approach could lead to more tailored and responsive patient management during and after surgery, potentially improving postoperative outcomes and reducing the overall complication rate associated with off-pump CABG.

Objectives and Endpoints

The following text was from the original protocol registered before the start of the trial.

Primary objective

To establish whether the care guided by cerebral and somatic tissue oxygen saturation monitoring compared to usual care reduces perioperative complications in patients having off-pump coronary artery bypass grafting surgery within 30 days of randomization.

Primary outcome measure

The primary outcome is a collapsed (one or more) composite of the following complications with a Clavien-Dindo grade II or greater arising within 30 days of randomization.

- Brain complications (postoperative delirium, cognition decline, stroke);
- Cardiac complications (non-fatal cardiac arrest, myocardial injury, heart failure, new-onset symptomatic ventricular arrhythmia);
- Respiratory failure;
- Renal complications (AKI stages II and III);
- Infectious complications (surgical site infection involving deep surgical site and/or organ/space, pneumonia, laboratory confirmed bloodstream infection, infection with source uncertain, and sepsis);
- Death.

Secondary objectives

To determine whether the care guided by $SctO_2$ and $SstO_2$ monitoring reduces various complications and duration of hospitalization.

Secondary outcome measures

- Components of the primary composite

- Atrial fibrillation, assessed within postoperative 30 days
- Postoperative delirium assessed from postoperative day 1 to 5
- Postoperative cognitive decline as a continuous variable assessed before surgery and on postoperative days 5 and 30

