The pragmatic trial design selected for the BOTTOMLINE-CS trial is rooted in its focus on evaluating the effectiveness of multisite tissue oxygen saturation monitoring in a real-world clinical setting. This approach emphasizes the applicability of the trial outcomes to typical clinical scenarios by ensuring that the study conditions closely mimic everyday practice. Unlike explanatory trials, which often employ strict participant selection and controlled conditions to determine efficacy under ideal circumstances, a pragmatic trial embraces broader eligibility criteria and diversity in participant characteristics, mirroring the variability seen in daily medical care. Furthermore, the implementation of interventions and monitoring within the usual care processes enables the assessment of the intervention's practical impact, including its feasibility, adherence, and overall utility in routine clinical workflows. The findings from such a pragmatic study are likely to be generalizable and thus informed clinical decision-making.

Sample Size Determination

The following paragraph was from the original protocol registered before the start of the trial. "We assume that the incidence of the composite 30-day complication in the regular care group will be 30% versus 24% in the multisite tissue oxygenation-guided perioperative care group, a 20% relative reduction representing a clinically meaningful and important treatment difference. Based on one-sided Z-test group sequential testing with 3 stages (two interim analyses) and boundary values calculated from O'Brien-Fleming Analog alpha (efficacy) and non-binding beta spending (futility) functions, a total of 927 patients will provide 80% power for detecting a 6% absolute reduction from 30% to 24% at a target alpha-level of 0.05. We plan to recruit 980 patients per group considering a potential ~5% of patients who drop out or have missing data."

Interim Analysis

The following is from the original protocol established before the start of the trial.

"For the interim analyses, O'Brien-Fleming Analog alpha and beta spending functions are used (Table 1, Figure 1). Assuming two interim analyses occur after 33% and 67% of total patients are enrolled and their primary outcome are observed, the nominal alpha levels to reject the null hypothesis for efficacy or fail to reject the null hypothesis for futility are calculated as follows.

Table 1. Critical values and alpha levels for two interim analyses and final analysis

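### The dropout Note is a censoring rule attached to a logistic model that cannot censor, and the SAP leaves undefined the 30-day outcome of an event-free patient lost before day 30

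*SAP*

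**What the plan says.** Four statements in the SAP bear on a patient lost before day 30.

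- **Outcome** (Primary outcome measure): a collapsed composite of "complications with a Clavien-Dindo grade II or greater arising within 30 days of randomization".
- **Model** (Analysis of the primary outcome): "The primary outcome will be evaluated using logistic regression to estimate the odds of postoperative composite complications". No time-to-event method is given for this outcome anywhere in the SAP.
- **Population** (Analysis Populations): the ITT definition reads "All randomized patients having at least some outcome data will be included in the analysis in the groups to which they were randomized". The Note in the same section adds: "Patients who were randomized and treated, but lost to follow up, will be included to the time of dropout".
- **Missing data** (Sensitivity Analysis): for the primary and secondary analyses, "we will exclude patients without outcome data", which the SAP labels an MCAR approach. It introduces the sensitivity analyses, including multiple imputation and best/worst case, with: "These analyses deal with the patients who did not have outcome data and the per-protocol population instead of ITT population".

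The SAP does not say whether a patient followed, for example, to day 8 has outcome data for a 30-day composite. It also does not say what value such a patient takes in the logistic model.

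**The concern.** Including a patient up to dropout makes sense when the analysis uses follow-up time. Logistic regression on a 30-day indicator does not. For a patient who is event-free when lost, the only value that the observed data can supply is 0, although the rest of the window was not seen.

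Partial ascertainment is a realistic prospect here. Cognitive decline is a component of the composite and cognition is tested on postoperative days 5 and 30, while infection and death can occur at any time in the window.

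If these patients enter as 0, two things follow. Their unobserved events are set to zero, which lowers the rate more in the arm with more loss. And because they now count as having data, the analyses meant to test sensitivity to missing outcomes pass over them. The rule would then bear on the primary result without any planned check on it.

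**Working it through.** **1. Reading the passages together**

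| Meaning of outcome data | ITT rule and Note | Exclusion rule | Result for an event-free dropout |
|---|---|---|---|
| Any follow-up counts | Patient is included | Does not apply | Enters as 0; not reached by imputation or best/worst case; the analysis is not the complete-case analysis that the SAP describes |
| Only a complete 30-day outcome counts | The Note has no effect on the primary analysis | Patient is excluded | Outcome missing; reached by imputation and best/worst case |

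The SAP does not choose between the rows. The ITT wording and the Note point to the first. The sample-size allowance points to the second: it treats about 5% of patients as lost to the analysis (927 / 0.95 = 976, planned as 980 per group).

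**2. Reproducing the plan's own figure**

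Inputs from the SAP: 30% versus 24%, 927 per group, three looks with efficacy bounds 3.710, 2.511 and 1.932, and a futility bound of 1.157 at the second look. Simulating the three-stage process with the futility stop applied gives power 0.809 to 0.810, against the stated 0.803. The design figures are therefore a sound base for what follows.

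**3. Effect of coding event-free dropouts as 0**

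Let p be the true 30-day rate, d the share lost, and f the share of dropouts' 30-day events seen before loss. The observed rate is p × (1 − d × (1 − f)). The SAP gives neither d by arm nor f, so both are assumptions.

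*Equal loss, d = 5%, f = 0 (the extreme):*
- Control: 0.30 × 0.95 = 28.5%. Intervention: 0.24 × 0.95 = 22.8%.
- The difference falls from 6.0 to 5.7 points, and the odds ratio moves from 0.737 to 0.741.
- Power with 980 per group is 0.836, against 0.843 for complete cases with 931 per group (futility stop ignored in both).

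*Unequal loss, no true effect (30% in both arms), 980 per group, more loss in the intervention arm.* SE = √[(p₁(1 − p₁) + p₂(1 − p₂)) / 980], with p₁ and p₂ the observed control and intervention rates. One-sided error at the final bound is Φ(−1.932 + difference / SE). With equal loss it is Φ(−1.932) = 0.027.

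| Loss, control vs intervention | f | Observed rates | Spurious benefit (points) | SE | One-sided error |
|---|---|---|---|---|---|
| 4% vs 6% | 0.5 | 29.40% vs 29.10% | 0.30 | 0.0206 | 0.037 |
| 4% vs 6% | 0 | 28.80% vs 28.20% | 0.60 | 0.0204 | 0.051 |
| 3% vs 7% | 0.8 | 29.82% vs 29.58% | 0.24 | 0.0206 | 0.035 |
| 3% vs 7% | 0.5 | 29.55% vs 28.95% | 0.60 | 0.0206 | 0.051 |
| 3% vs 7% | 0 | 29.10% vs 27.90% | 1.20 | 0.0204 | 0.090 |

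Counting all three looks changes little: the base becomes 0.028, the 4% versus 6% rows 0.039 and 0.053, and the 3% versus 7% rows 0.053 (f = 0.5) and 0.093 (f = 0).

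**4. The other shortcut is also biased**

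Suppose pre-dropout events are kept but event-free dropouts are deleted. The rate becomes p(1 − d(1 − f)) / (1 − d(1 − pf)). With p = 0.30, f = 0.5 and 3% versus 7% loss:
- Control: 0.2955 / 0.9745 = 30.3%.
- Intervention: 0.2895 / 0.9405 = 30.8%.

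A spurious benefit of 0.6 points turns into a spurious harm of about 0.5 points. The handling of a few patients can reverse the direction of the bias, so it should be fixed in advance.

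**The case against.** The strongest reply is that the SAP nowhere says event-free dropouts are coded as complication-free. The Note stands under Analysis Populations and governs every outcome. Several outcomes are complete well before day 30: delirium on days 1 to 5, cognition on day 5, and length of stay for patients already discharged. The Note may mean only that a patient contributes the outcomes assessed before loss and drops out of the rest. The 5% allowance fits that reading. This stands: the 0 coding is the natural consequence of the Note and the ITT rule, but it is not a stated rule.

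A reader might also infer that the SAP contradicts its own complete-case rule and, at the same time, hides these patients from the sensitivity analyses. The documents do not support both. The contradiction needs partial follow-up not to count as outcome data; the escape from imputation needs it to count. Only one can be true, and the SAP does not say which.

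The size is open to challenge too. Nothing in the SAP suggests unequal loss. With f = 0, no dropout's event is seen before loss, which is extreme for a patient lost after the early postoperative assessments. Patients who withdraw consent are left out of the analysis altogether, so the loss governed by the Note may be below 5%. All this lowers the likely effect.

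It does not remove the point. The SAP itself states the Note, the ITT rule and the exclusion rule, and they do not together settle one value for an included patient in the primary model.

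**Conclusion.** The point holds as an undefined rule that, read naturally, can bias the primary result; it should be corrected. It is neither a stated instruction to count dropouts as complication-free nor a proven contradiction with the missing-data section.

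With equal loss of about 5% the effect is negligible. With unequal loss the bias favours the arm that loses more patients. The illustrative rise in one-sided error, from about 0.027 to between 0.035 and 0.09, rests on assumed loss by arm and an assumed share of events seen before loss. The value of 0.09 is an upper scenario, not an expectation.

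**What to change.** Replace the Note and align the ITT definition with it:

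- Define outcome data for the primary composite as a qualifying event (death included) at any time in the window, or ascertainment complete to day 30.
- A qualifying event before dropout counts as an event.
- A patient event-free at dropout with incomplete 30-day ascertainment has a missing primary outcome, never a non-event, and enters the planned multiple imputation and best/worst-case analyses.
- For the primary estimate, either use multiple imputation for these few patients, or keep a complete-case analysis restricted to patients with full 30-day ascertainment (deaths included) and report the imputed result beside it. Do not keep pre-dropout events while deleting event-free dropouts, for the reason shown in step 4 of the working.
- Report the number of such patients by arm.

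The cost is SAP wording and one derived missing-outcome flag. If imputation moves into the primary estimate, it also changes the planned primary analysis, which then relies on imputation for a few patients. The second option avoids that change. The SAP was written after recruitment had closed but with follow-up still running, a stage at which this rule could be fixed.
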